The Effect of Intravenous EACA on Blood Loss and Transfusion Requirements After Bilateral VRO

Protocol and Analysis Plan

NCT # NCT02257580

Approved 12/10/2014

1. What is the Study Design

Experimental:

Randomized controlled clinical trial (RCT)

2. Who will be recruited and enrolled?

Inclusion Criteria:

Patients will be recruited from the practices of [name] and [name]. Inclusion criteria will include the following:

- Age less than or equal to 18
- Scheduled for elective bilateral VRO with or without associated soft tissue and osseous procedures

Exclusion Criteria:

All patients will be asked to discontinue acetylsalicylic acid (ASA), antiplatelet agents, and hormone replacement and hormonal contraceptive agents at least 7 days prior to surgery. Other than ASA, these agents will be held 6 weeks postoperatively.

- Preoperative use of an anticoagulant (Plavix, warfarin, lovenox, etc.)
- History of hypersensitivity to EACA
- History of thromboembolic event (e.g., PE or DVT)
- History of renal insufficiency or failure
- Congenital or acquired coagulopathy as evidence by INR >1.4 or PTT > 1.4 times normal, or Platelets <150,000/mm³ on preoperative laboratory testing
- Use of hormone replacement therapy or hormonal contraceptive agent within 7 days prior to surgery
- Pregnant
- Breastfeeding
- Older than 18 years of age
- Patients not receiving neuraxial anesthesia

This trial will be registered on ClinicalTrials.gov. All patients undergoing bilateral VRO by the study surgeons ([name]) will be identified in their office and screened for eligibility as potential patients for participation in the study. A research assistant will review the office and operative calendars of the study surgeons each week to identify and recruit potential patients. The assistant will record on the CONSORT diagram any reasons for ineligibility/exclusion.

The surgeon, a co-investigator or research assistant will obtain consent prior to surgery, at the patient's preadmission screening visit. All authors on the protocol, in addition to their research assistants, will be designated to obtain consent.

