Bilateral VRO will be performed as per the surgeon's routine practice. In general, the operative extremity will be prepped and draped in the usual sterile fashion. Prior to incision, the anesthesiologist will administer a loading dose of 100 mg/kg of EACA with a max of 4-5 grams up to 1 hour prior to incision. During the case, an infusion of 33 mg/kg/hr (max of 1 gram/hr) will be maintained. The use of EACA will be terminated at the end of the case. Patients randomized to the placebo arm will be

infused with a comparable volume of normal saline prepared by the pharmacy. All participating anesthesiologists will not be blinded in this study. A direct lateral approach to the femur will be used, and standard surgical techniques for intra-operative hemostasis will be utilized. The surgeon will perform bilateral femoral osteotomies and associated soft tissue surgery and pelvic osteotomy. After all hardware is placed, the wound will be thoroughly irrigated and suctioned. A deep drain will be placed on each operative side, and the wound will be closed in layers. Intra-operatively, a cell saver will be used, and the volume (mL) of auto-transfusion will be recorded.

Hematocrit levels will be monitored regularly in the post-operative period. As per protocol, a post-op hematocrit will be drawn in the PACU, and subsequently, daily labs will be obtained unless specified by the medicine or surgical attending. Routine, daily inpatient CBC data and drain output will be reviewed. Inpatient and office records will be accessed to help identify postoperative complications. The criteria for transfusion of blood products will be a hemoglobin level of < 7.0 g/dL or a hemoglobin level of < 10.0 g/dL with clinical signs of symptomatic anemia (e.g., unexplained tachycardia, hypotension unresponsive to fluids or vasopressors, change in mental status, low urine output, and shortness of breath). Blood will be administered 1 unit at a time, and the presence of symptoms or signs will be reassessed after each unit. This algorithm may be altered by the treating physician (e.g., PACU attending, surgeon, pediatrician, or the OR anesthesiologist), however all decisions will be supported by reasonable documentation. Drains will be removed on POD 2 unless specified by the attending surgeon, and the 24-hour clock will begin once the patient is in the PACU. All drains, patient charts, and patient rooms will be clearly labeled in order to identify study patients.

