All tests and imaging used in this study are considered standard of care.

Randomization Process:

The patients will be randomized into one of 2 groups: (1) Loading dose and infusion of EACA (2) Equivalent volume of normal saline prepared by the pharmacy. An EACA loading dose of 100 mg/kg with a max of 4-5 grams will be given up to 1 hour prior to incision. During the case, an EACA infusion of 33 mg/kg/hr (max of 1 gram/hr) will be maintained. The use of EACA will be terminated at the end of the case. Assignment of patients will be made based on a sequential treatment assignment or minimization strategy in order to ensure an even distribution of patients in each treatment arm. More specifically, each patient will be randomized to the treatment arm that would minimize differences between groups. Randomization will be stratified by sex and surgery type (bilateral VRO, bilateral VRO with associated soft tissue or osseous procedure) so that the number of male/female patients and VRO/associated procedure patients will be balanced in each study group between trial arms.

The Biostatistics Core of the HSS Healthcare Research Institute will randomize each patient based on the minimization strategy. It will be a double-blind experiment with all parties, except the pharmacy, anesthesiologist, and designated research assistant, being blinded to the randomization schedule (surgeon, medical staff, and patient). Patient recruitment will continue until a total of 30 patients are enrolled.

Treatment Groups:

Bilateral VROs will be performed as per the study surgeon's routine practice. In general, the operative extremity will be prepped and draped in the usual sterile fashion. Prior to incision, the anesthesiologist, will administer a loading dose of 100 mg/kg of EACA with (max of 4-5 grams) or an equivalent volume of normal saline prepared by the pharmacy. The loading dose may be give up to 1 hour prior to incision. During the case, an EACA infusion of 33 mg/kg/hr (max of 1 gram/hr) will be maintained. Only anesthesiologists agreeing to participate in the study will be paired with the study surgeons, and all anesthesiologists will be aware of a patient's randomization to the treatment or placebo group.

Outcome Measures

Primary outcome: Calculated total blood loss.

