VTE prophylaxis is not commonly used for pediatric patients at our institution. However, all patients will also receive a comprehensive approach to postoperative care comprised of mechanical (sequential compressive device) prophylaxis in-house, early mobilization with physical therapy, medical optimization, and regional anesthesia (if appropriate).

4. What is the long-term significance?

There are certain risks associated with blood loss and blood transfusion after elective orthopaedic procedures in young patients. Blood loss and transfusion requirements can be reduced with several blood conservation measures, including the use of pharmacological agents such as EACA. If the use of IV EACA is shown to decrease blood loss and transfusion requirements after bilateral VROs, it will provide an efficacious and inexpensive method to reduce post-operative morbidity and improve patient outcomes after bilateral VROs.

D. SAMPLE SIZE AND DATA ANALYSIS

Sample Size -

- 1. Proposed analysis (e.g., student's t-test, ANOVA, chi-square, regression, etc.): Independent samples t-test will be utilized if the data is normally distributed (or non-parametric Mann-Whitney U test if assumption of normality is not met).
- 2. Alpha level: 0.05
- 3. Beta or power level: 0.81
- 4. Primary outcome variable estimate (mean +/- s.d. for continuous outcome, frequency/percentage for categorical variable):

The primary outcome of interest in total intra-operative blood loss, which will be summarized as mean +/- standard deviation. Based on an analysis of the twenty-four consecutive cases of bilateral VROs, the mean calculated intra-operative blood loss was 671.24mL (SD: 233.69).

- 5. Number of groups being compared (use 1 for paired analysis within the same subjects): Two groups are being compared: Treatment Group (Loading Dose + Infusion) vs. Placebo Group (NS)
 - 6. Effect size or change expected between groups: 250cc

- 7. Resulting number per group: 12
- 8. Total sample size required: 24

Data Analysis

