The primary outcome of interest (calculated total blood loss) will be presented as a mean +/-standard deviation and compared between the EACA and placebo groups with a two-sample t-test. Multivariable linear regression models will also be used to adjust for any potential confounding due to total blood loss volume between arms after adjustment for age, sex, BMI, and anesthesia type. To adjust for any patients lost due to early withdrawal, we will increase our sample size by 3 patients in each group for a total sample size of 30 patients.

Calculated total blood loss will be determined from the difference between the preoperative hemoglobin and the postoperative hemoglobin (or the lowest postoperative hemoglobin during the hospital stay prior to transfusion). Based on hemoglobin balance, the estimated blood loss will be calculated according to the formula by Nadler et al.¹⁷:

```
Estimated Blood Volume (EBV) = (k_1 \text{ x Height}^3 \text{ (m)}) + (k_2 \text{ x Weight (kg)}) + k_3
For men, k_1 = 0.3669, k_2 = 0.03219, and k_3 = 0.6041
For women, k_1 = 0.3561, k_2 = 0.03308, and k_3 = 0.1833
```

Multiplying the EBV by the hematocrit (Hct) gives the red blood cell (RBC) volume. As such, a change in the RBC volume can be calculated from a change in the Hct level^{23,24}:

```
Total RBC volume loss = EBV \times (Hct Preop - Hct Postop)
```

Transfusions (mean volume per unit at HSS, 250 mL) can be taken into account by calculating the total blood loss¹⁶:

Total blood loss (L) = Total RBC volume loss + (No. of Units Transfused x 0.25) / (Hct Preop – Hct Postop) / 2)

All continuous secondary outcomes such as postoperative allogeneic blood transfusion requirement, intraoperative cell saver utilization, and length of hospital stay, will be analyzed in the same manner as the primary outcome.

Complications will be reported as incidence rates with 95% confidence intervals.

All hypotheses will be evaluated with two-sided tests with statistical significance set at $\alpha = 0.05$.

Bibliography

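### The surgery-type minimisation factor codes soft-tissue and osseous additions alike, leaving added bone surgery to chance between the arms

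*Combined protocol and SAP*

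**What the plan says.** All places are in the combined protocol and SAP.

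- **Allocation (section 3, Randomization Process).** Patients are allocated by minimisation: "each patient will be randomized to the treatment arm that would minimize differences between groups". There are two factors: "Randomization will be stratified by sex and surgery type (bilateral VRO, bilateral VRO with associated soft tissue or osseous procedure". The same sentence gives the aim: "so that the number of male/female patients and VRO/associated procedure patients will be balanced in each study group between trial arms". That aim confirms that surgery type has two levels, VRO alone and VRO with any addition.
- **Eligibility (section 2, Inclusion Criteria).** "Scheduled for elective bilateral VRO with or without associated soft tissue and osseous procedures".
- **Description of the operation (section 3).** "The surgeon will perform bilateral femoral osteotomies and associated soft tissue surgery and pelvic osteotomy". Pelvic osteotomy is thus one of the possible additions. Read literally, the sentence gives it to every patient.
- **Analysis (section D, Data Analysis).** The primary outcome is "compared between the EACA and placebo groups with a two-sample t-test". A regression is also planned, "after adjustment for age, sex, BMI, and anesthesia type". Surgery type is not among these covariates.
- **Data collection (section 3, lists of data to be recorded).** The operating-room list covers anesthetic, operative time, transfusion, cell saver and complications. The associated procedures performed are not listed.

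**The concern.** Surgery type is one of only two factors chosen for balancing, so the plan itself treats surgical extent as something the arms should share. Yet the cut separates no addition from any addition, and does not separate bone from soft tissue. It is plausible that additional osteotomies change blood loss more than a soft-tissue release does. If so, the arms can be balanced on the coded factor and still differ in the amount of bone surgery. If most patients have some addition, nearly everyone falls in one level and the factor balances very little.

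No later step compensates. The t-test is unadjusted and the regression omits surgery type. Adding the factor as now coded would not help, because both kinds of case carry the same code. Without a record of the procedure performed, an imbalance might not even be visible in the report. At stake are the comparability of two arms of about 15 and the precision of the primary contrast.

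**Working it through.** The plan states no figure for this imbalance, so there is none to reproduce.

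**Inputs from the documents.** 30 patients, 15 per arm; target difference 250 mL; SD 233.69 mL from 24 consecutive cases, not split by procedure.

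**Assumed inputs.** Case mix; sex 50/50; added loss per osseous procedure of 150-300 mL, with 100 mL as a lower check; minimisation that always takes the better arm, with ties broken at random. The plan does not say whether a random element is used.

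**Step 1: chance imbalance under the two-level factor.** Simulation of 30-patient trials, 5,000-6,000 per scenario:

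| Assumed mix: VRO alone / soft tissue only / osseous (%) | Arms differ by 3 or more osseous cases |
|---|---|
| Four mixes: 20/40/40, 10/40/50, 30/35/35, 10/60/30 | about 27-34% |
| 50/25/25 | 21% |
| 10/10/80 | 16% |
| 5/5/90 | 6% |

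For the four mixes in the first row, a difference of 4 or more occurs in 13-18% of trials. The SD of the between-arm difference in the osseous proportion is about 0.15-0.18.

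**Step 2: what the present factor achieves.** For the 20/40/40 mix, simple randomisation gives an SD of sqrt(2 x 0.4 x 0.6 / 15) = 0.179. Under the plan's factor it is 0.167, so little of the chance imbalance in osseous cases is removed.

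**Step 3: shift in the arm difference.** Shift = difference in osseous proportion x added loss.

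- Typical (1 SD): 0.15 x 150 = 22.5 mL to 0.18 x 300 = 54 mL, or 9-22% of 250 mL. At 100 mL added loss it is 15-18 mL.
- Less common, a 4-case difference: 4/15 x 150 = 40 mL to 4/15 x 300 = 80 mL, or 16-32% of 250 mL. At 100 mL it is 27 mL, or 11%.

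**Step 4: compare with the standard error.** 233.69 x sqrt(2/15) = 85 mL. The typical shift is therefore 22.5/85 = 0.26 to 54/85 = 0.64 of one standard error.

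**Step 5: what adjustment could recover.** Suppose the 24 historical cases had 40% osseous procedures (an assumption). The SD then already contains a component of 0.4 x 0.6 x (added loss)². That is 5,400 at 150 mL and 21,600 at 300 mL, out of 233.69² = 54,611. Removing it gives:

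- 150 mL: sqrt(54,611 - 5,400) x sqrt(2/15) = 81 mL
- 300 mL: sqrt(54,611 - 21,600) x sqrt(2/15) = 66 mL

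The standard error would fall from 85 mL to between 81 and 66 mL, before the small loss of degrees of freedom.

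**Step 6: alternative cuts.**

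| Factor | Osseous cases 3 or more apart | VRO-alone cases 3 or more apart |
|---|---|---|
| Plan (two levels) | about 27-34% | about 0% |
| Osseous yes/no | 0% | about 10-26% |
| Three levels | about 0.2% or less | about 0.2% or less |

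For the 20/40/40 mix, the mean absolute difference in osseous cases falls from 1.95 with two levels to 0.59 with three.

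**The case against.** The strongest reply is that this is ordinary chance variation. Within a level, assignment does not depend on which addition the child has, so the estimate is not biased, and the t-test's standard error already allows for such variation. If the historical cases had a similar mix, the SD of 233.69 mL includes it. This stands. A reader might infer from the imbalance that the trial is biased, and nothing in the documents supports that.

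A reader might also infer that bone surgery is the main driver of blood loss and that soft-tissue additions are minor. The documents give no loss by procedure. Their own outcome formula points to another strong driver, because the hematocrit change is multiplied by estimated blood volume. For illustrative boys of 1.0 m and 15 kg and of 1.7 m and 60 kg, that volume is 1.45 L and 4.34 L, about a threefold range. Only the weaker premise, that added bone surgery plausibly affects loss, is used here.

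The case mix is also assumed, and the problem shrinks as osseous surgery becomes nearly universal. If everyone has a pelvic osteotomy, as the description of the operation can be read, a split by osseous procedure has nothing to balance. But that reading conflicts with the eligibility criterion and with the two levels of the factor, so it cannot be taken as settled.

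Finally, near-zero imbalance after re-cutting is close to automatic, because it measures balance on the factor just inserted under deterministic minimisation. With an 80% biased coin, an osseous yes/no factor still left 3 or more cases apart in about 7% of trials. A yes/no cut also moves imbalance to the VRO-alone cases. Better balance without adjustment leaves the t-test's standard error unreduced. These points are sound, and they are why three levels and a model term are proposed.

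**Conclusion.** The point holds as a limited design weakness. The text places soft-tissue and osseous additions in one level, nothing elsewhere separates them, and no planned analysis uses surgery type. With 30-50% osseous cases (assumed), about 27-34% of 30-patient trials would have arms 3 or more osseous cases apart; at 80% osseous, about 16%. At an assumed 150-300 mL per osseous procedure, the typical shift is about 23-54 mL, against a standard error of about 85 mL. That is a loss of precision and comparability, not systematic bias. The textual finding needs no assumption. The millilitre figures depend wholly on the assumed mix and added loss. The change is worth making because it is cheap, not because the trial would otherwise be invalid.

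**What to change.** 1. **Randomization Process, section 3.** Define surgery type by planned procedure in three levels: bilateral VRO alone; with soft-tissue procedures only; with any osseous procedure, alone or combined with soft-tissue work. State the aim of balance in the same terms. This assumes the planned procedure is known at allocation, which the present factor also requires.
2. **Data lists, section 3.** Add the associated procedures actually performed to the operating-room record, and tabulate them by arm.
3. **Data Analysis, section D.** Add the three-level planned-procedure factor to the regression, so that the better balance is reflected in the standard error.
4. **Reconcile the text.** The description of the operation, the inclusion criterion and the factor's levels disagree on whether every patient has a pelvic osteotomy. They must be brought into agreement.

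**Cost.** A line in the minimisation set-up, one data field and two extra model terms; no added patients or visits. The downside is one more factor level, with slightly looser balance in overall arm size.

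### The plan gives two different primary tests and adds regression models at the same 0.05 level, without saying which analysis decides

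*Combined protocol and SAP*

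**What the plan says.** Three statements bear on the test of the primary outcome, calculated total blood loss.

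- Section D, Sample Size, item 1: "Independent samples t-test will be utilized if the data is normally distributed (or non-parametric Mann-Whitney U test if assumption of normality is not met". The normality check is not named, and neither its threshold nor the data it applies to (each arm, pooled values or residuals) is given.
- Section D, Data Analysis: the outcome is to be "compared between the EACA and placebo groups with a two-sample t-test". No switch is mentioned.
- The same paragraph: "Multivariable linear regression models will also be used", with adjustment for age, sex, BMI and anesthesia type.

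The level is common to all of them: "Alpha level: 0.05" under Sample Size, and "All hypotheses will be evaluated with two-sided tests with statistical significance set at" 0.05 at the end of Data Analysis. Continuous secondary outcomes are to be handled in the same way as the primary one, so they inherit whatever is unclear about it. Under Randomization Process in section 3, allocation is balanced on sex and on surgery type.

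**The concern.** If the data look non-normal, the two parts of section D cannot both be followed: one calls for Mann-Whitney, the other for the t-test. The regression then gives a further p-value for the same outcome at the same level, and nothing calls it supportive or says what happens if it conflicts with the simple comparison. Its role cannot be settled from its stated purpose either, because the sentence names blood loss itself, the outcome, as the source of confounding.

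The conclusion of a small trial could therefore depend on which analysis is put forward after the data are seen. In addition, after a switch to ranks the deciding test would no longer be a test of the 250 mL mean difference on which the trial is sized.

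**Working it through.** **Inputs from the documents.** Mean 671.24 mL and SD 233.69 mL (Sample Size, item 4); "Effect size or change expected between groups: 250cc"; "Beta or power level: 0.81"; 12 per arm, raised to 15 per arm for withdrawals; two-sided 0.05; sex balanced between arms.

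**Assumptions, not in the documents.** Covariates explain 0-60% of outcome variance (0-50% for the switched-test figures). The outcome is normal or lognormal. Anesthesia type has three levels, so the regression has five covariate terms. The normality check is Shapiro-Wilk.

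**Step 1, the plan's own figure.** The standard error of the difference at 12 per arm is 233.69 × √(2/12) = 95.4 mL, and 250/95.4 = 2.62. With 22 degrees of freedom the two-sided t-test has 70.7% power; a one-sided test has 81.4%. At 15 per arm the standard error is 233.69 × √(2/15) = 85.3 mL, the ratio is 2.93, and two-sided power is 80.7%. The stated 81% at 12 per arm thus does not reproduce two-sided. That is a separate matter, but it confirms that the sizing rests on a t-test of a mean difference.

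**Step 2, false-positive rate by rule.** For two tests each at 5%, the chance that at least one is significant lies between 5% (always agreeing) and 10% (never significant together); independence would give 1 − 0.95² = 9.75%. The t-test and the regression share the same outcome data, so the answer falls between. Simulation with no effect, normal data, sex balanced, 20,000 trials per row:

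| Per arm | Variance explained | t-test alone | Regression alone | Either |
|---|---|---|---|---|
| 12 | 0 | 4.96% | 5.19% | 7.19% |
| 12 | 30% | 4.00% | 4.95% | 7.12% |
| 12 | 60% | 2.81% | 5.16% | 6.98% |
| 15 | 0 | 5.07% | 5.04% | 6.76% |
| 15 | 30% | 3.87% | 4.85% | 6.69% |
| 15 | 60% | 3.04% | 4.88% | 6.84% |

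In the first row, 4.96 + 5.19 − 7.19 = 2.96% of trials are significant on both. The t-test falls below 5% as covariates matter more because it ignores the balancing on sex.

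With the normality-switched test in place of the t-test, the either-test rate is about 6.5-8%. The switched test alone gives 3.0-5.6%. Counting the t-test or the switched test, without the regression, gives 3.1-5.9%. So the regression, not the switch, produces the excess.

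**Step 3, how often the switch is used.** A check at 0.05 in each arm would trigger in about 1 − 0.95² = 9.75% of trials with normal data. Simulation gives 9-10%, and about 30-39% with lognormal data of the same mean and SD.

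**Step 4, conflict under a true 250 mL effect.** Over 0-50% of variance explained, the switched test and the regression fall on opposite sides of 0.05 in roughly 16-23% of trials at 12 per arm and 11-15% at 15 per arm. Single scenarios can lie a point or so outside these ranges through simulation error.

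**Step 5, which model could decide.** At 12 per arm, when covariates explain nothing, the five-term regression cuts power from about 71% to 61%. It also omits surgery type, a balancing factor. It includes anesthesia type, which may be settled only in the operating room: section 3 keeps a patient in the study if a combined block fails and another succeeds, and the anesthesiologist knows the arm. A model with sex and surgery type adds two terms, leaving 24 − 4 = 20 residual degrees of freedom instead of 22, or 26 instead of 28 with 30 patients.

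**The case against.** The strongest reply is that the plan already has a natural order. The t-test comes first in Data Analysis, it is the default in item 1, and section 2 sizes the trial on it. The regression is introduced as an addition with a limited purpose. On that reading one test decides and the error rate is 2.8-5.5% (t-test) or 3.0-5.6% (switched test). This is a fair reading, and it stands as the most likely intention. It still leaves item 1 and Data Analysis in conflict when the data are non-normal, and the order is inferred, not stated.

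Three stronger readings are tempting, and the documents do not support them.

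- A reader might infer that the trial's actual false-positive rate is 7-9%. That needs a rule that any significant analysis counts as success. The plan does not exclude such a rule, but it does not state one. Values up to 9.7% arise only if sex is left unbalanced, contrary to the allocation scheme, and Mann-Whitney is always counted.
- Because the plan speaks of regression models in the plural, a reader might count several. Four nested models would give 7.9-10.1%, but the plan gives a single covariate list and no such set.
- A reader might infer that a switch to ranks leaves no result in mL. It does not: the outcome is summarised as mean and standard deviation whichever test is used, and the linear regression gives and tests an adjusted difference in mL.

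It is also fair to say that the normality check is weak at this size rather than arbitrary, since it triggers three to four times as often with lognormal as with normal data.

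**Conclusion.** The concern holds as an undefined decision rule, not as a demonstrated inflation of the error rate. Section D prescribes two different primary tests, adds regression at the same two-sided 0.05, and does not say which decides. What is at stake is about 5% or less if one analysis decides, against about 6.5-8% if either the switched test or the regression may be claimed. With the planned effect real, the chance of two opposite answers with no rule between them is roughly 16-23% at 12 per arm or 11-15% at 15 per arm. These sizes rest on the assumed covariate strength, outcome shape, normality check and three anesthesia levels, and on balanced sex. The normality switch adds almost nothing to the error rate; its defects are the contradiction between the two parts of section D and a deciding test that no longer matches the sizing. This should be corrected before unblinded data are analysed.

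**What to change.** State the same single deciding analysis under Sample Size, item 1, and under Data Analysis, and delete the normality switch. Suggested content: a linear model for calculated total blood loss with arm, sex and surgery type (the two factors on which allocation is balanced), reported as a mean difference in mL with 95% CI and two-sided p-value.

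Label the unadjusted t-test, the Mann-Whitney test and the regression on age, sex, BMI and anesthesia type as sensitivity analyses that do not decide the conclusion. Say whether the continuous secondary outcomes follow the same model.

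Retaining the plain t-test as the deciding analysis would also remove the ambiguity. The model is preferable because it uses the balancing factors, which the t-test ignores at the price of a conservative error rate when sex is predictive.

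Cost: wording only, with no added patients or procedures. The model uses two degrees of freedom, and the freedom to choose the test after seeing the data is given up.
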